15.7 Health Related Quality of Life (CALGB 70702)

Hypothesis A: Patients in the hyperfractionated accelerated dose (45 Gy) group will experience worse lung cancer specific physical symptoms and physical functioning, as measured by the FACT TOI (Trial Outcome Index) -Lung Cancer and FACT-Esophageal Cancer Eating and Swallowing Indices, than those in the high dose daily (70 Gy) and concomitant boost radiotherapy (61.2 Gy) groups when all RT has been completed in each arm of the study at 12 weeks after the start of radiation therapy. This hypothesis will be revised to reflect the change in the research design due to the elimination of one of the experimental arms (high dose daily or the concomitant boost radiotherapy arm), due to greater toxicity.

Hypothesis B: Patients in the hyperfractionated accelerated dose (45 Gy) group will experience worse esophagitis (measured by the ECOG Acute Esophagitis Scale and difficulty swallowing item), and as a consequence worse psychological state, (measured by the Hospital Anxiety and Depression Scale), and lower quality-adjusted life years (measured by the EQ-5D) than those in the high dose daily (70 Gy) and concomitant boost radiotherapy (61.2 Gy) groups when all RT

has been completed in each arm of the study. This hypothesis will be revised to reflect the change in the research design due to the elimination of one of the experimental arms (high dose daily or the concomitant boost radiotherapy arm), due to greater toxicity.

Hypothesis C: Patients in the high dose daily 70 Gy arm of the study will experience greater treatment inconvenience (measured by a single item developed for this study), than those in the other two arms of the study, due to having to come into clinic for 7 weeks, the longest duration of the three arms. If the 70 Gy arm is eliminated due to greater treatment toxicity, then this hypothesis will be revised to reflect that those in the 61.2 Gy arm will experience greater treatment inconvenience than those in the 45 Gy arm, due to having to come into clinic for 5 weeks.

Overview:

In the quality of life companion, patients will be assessed by multiple HRQOL (Health-related quality of life) scales at baseline, 3, 5, 7, 12, 26 and 52 weeks (see [Table 1](#) for details). Investigators are interested in evaluating the change of quality of life assessments from baseline to multiple time points during and after treatment and comparing the differences of such changes between treatment regimens. It is expected that patients in arm 1 (45 Gy) experience worse physical and functional well being, worse esophagitis than those in the remaining study arm (arm 2 or 3), and that patients in arm 2 (70 Gy) experience worse treatment inconvenience than those in arm 1 (45 Gy) or arm 3 (61.2 Gy). The HRQOL scores changed from baseline to 12 week are of the primary scientific interest. The size of the HRQOL companion is chosen such that one has adequate power to test three sets of scientific hypotheses as shown in Table 2). The companion will register 415 patients (57%) from the 729 patients consenting to the main treatment study. Of the 415 patients, 394 patients are expected to meet the eligibility criteria. Of the 394 patients on the companion study, 188 patients are expected in each of the two remaining study arms and 18 patients are in the discontinued study arm.

Table 2
Quality of Life Assessment

QoL Endpoint Variable	Hypothesis	Measure	Statistical Analysis

Primary Endpoints Physical Well-being, Functional Well-Being, Lung Cancer physical symptoms
 
FACT Esophageal Eating and Swallowing Subscales
	
Hypothesis A: At 12 weeks after the start of XRT, patients in the 45Gy arm will report worse physical symptoms and functioning than those in the high dose daily (70Gy) and concomitant boost RT (61.2 Gy) groups.
	
FACT-L (TOI)
 
FACT Esophageal Eating and Swallowing Subscales
	
Continuous scores/outcomes
 
T test; Analysis of covariance; Linear mixed effect model or general linear model with generalized estimating equations


Secondary Endpoints
 
Esophagitis
	
Hypothesis B: At 12 weeks after the start of XRT, patients in the 45Gy arm will experience worse esophagitis than those in the high dose daily (70Gy) and concomitant boost RT (61.2 Gy) groups.
	
ECOG Acute Esophagitis Scale
 
Difficulty swallowing
	
Dichotomized or ordinal scores/outcomes
 
Chi-square test; Logistic regression; Nonlinear mixed effect or generalized linear model with generalized estimating equations using log or multi-log link.

Psychological state
	
Hypothesis B: At 12 weeks after the start of XRT, patients in the 45Gy arm will report a worse psychological state than those in the high dose daily (70Gy) and concomitant boost RT (61.2 Gy) groups.
	
Hospital Anxiety and Depression Scale (HADS)
	
Continuous scores/outcomes
 
T test; Analysis of covariance; Line mixed effect model or general linear model with generalized estimating equations

Quality-adjusted Life Years (QALY)
	
Hypothesis B: At 12 weeks after the start of XRT, the QALY of those in the 45 Gy will be worse than those in the high dose daily (70Gy) and concomitant
	
EQ-5D
	
Quality adjusted time to event variable/outcome
 
Generalized log rank test for QALY data

	boost RT (61.2 Gy) groups.		
Treatment Inconvenience	Hypothesis C: At 7 weeks after the start of XRT, treatment inconvenience will be greatest for those receiving 70Gy QD in 7 weeks.	Single item developed for the study	Dichotomized or ordinal scores/outcomes Chi-square test; Logistic regression; Nonlinear mixed effect or generalized linear model with generalized estimating equations using log or multi-log link.

Refusal and attrition rates have been found to vary by disease site, stage, type of treatment, method of data collection, and length of follow-up. Osoba and Zee [78] conducted a review of completion rates in health-related quality of life assessments of the National Cancer Institute of Canada Clinical Trials Group, in which data were collected by self-administered questionnaires. In seven completed trials, quality of life completion rates were high with more than 93% of patients completing questionnaires at baseline and while on treatment. The rate of completion off treatment was 85%. In Ganz et al.’s [90] study of the quality of life of early stage Hodgkin’s disease patients, in which data was collected by mailed questionnaires, the completion rate by the second year was 70%. In a Gynecologic Oncology Group study of the quality of life of endometrial cancer patients randomized to either laparoscopy vs. laparotomy, in which data were collected by self-administered questionnaires, the completion rate by 6 months was 85% [91]. In a Cancer and Leukemia Group B study of patients with myelodysplastic syndrome treated by 5-Azacytidine (CALGB 9221) in which patients were interviewed by telephone about their quality of life, only 5% refused to continue the quality of life assessments over a 6 month study period [92]. In the Gynecologic Oncology Group trial of IP versus IV chemotherapy in ovarian cancer patients, where patients completed questionnaires in the clinic, 82% of IV and 79% of IP patients completed self-administered questionnaires at 12 months after treatment. Therefore, given these findings, it is reasonable to assume a completion rate of quality of life data of at least 80% at both baseline and 12 weeks after the start of radiation therapy, which ensures adequate statistical power in conducting the planned comparisons at the designated levels of effect size and Type I errors.

Power Analysis:

The following assumptions are made in the power calculations: (1) Based on the literature and previous CALGB studies, we expect that at least 80% of eligible patients who register to the companion will complete the HRQOL assessments at both baseline and 12 weeks after the start of radiation therapy. That is, of the 394 eligible patients on the companion study, 150 patients in the two remaining study arms and 15 in the discontinued study arm will have complete HRQOL assessments at both baseline and 12 weeks after the start of radiation therapy; (2) Within each set of hypothesis (A, B, C), Type I error will be controlled at the level of 0.05. The Bonferroni method is used to address the issue of multiple comparisons for simplicity and reasonable performance with a small number of comparisons; and (3) Two-sided tests will be used.

Hypothesis A

Three planned comparisons will be made to address Hypothesis A. The total TOI score from FACT TOI, the eating score and the swallowing score will be calculated from the FACT-Esophagus Subscale. The change scores between baseline and 12 weeks after the start of radiation therapy are of interest. A size of 150 patients with complete assessments at baseline and 12 weeks after the start of radiation therapy in each of the two remaining arms will have 85% power to detect an effect size of 0.397 s.d. unit on the scale of change score using a two group t-test at a significance level of 0.0167 (0.05/3). The effect size of 0.397 s.d. is usually associated with a moderate effect in quality of life literature.

Hypothesis B

Five comparisons will be made to address this hypothesis - ECOG esophagitis score (severe/ ≥ 7 vs moderate/ < 7), difficulty swallowing (severe/ ≥ 4 vs. moderate/ < 4), HADS depression score, HADS anxiety score, and quality-adjusted life year (QALY).

The ECOG esophagitis score ranges from 0 to 12 points. We will define patients with scores of ≥ 7 as “Severe” and score < 7 as “Moderate.” With 150 patients in each remaining arm with complete assessments at baseline and 12 weeks after the start of radiation therapy, a two group continuity corrected Chi-square test at a 2-sided significance level of 0.01 (0.05/5) will have 80% power to detect the 18% difference of the proportions of patients with severe symptoms between the two remaining study arms, assuming 35% of patients in arm 1 report severe symptoms and 17% in the other remaining arm (odds ratio of 2.625).

We define swallowing difficulty score as 4 or 5 as “Severe” and scores 1, 2, or 3 as “Moderate.” Similar to the ECOG esophagitis score, with 150 patients in each study arm, we have 80% power to detect a 18% difference of severe swallowing difficulty between the two study arms, assuming 35% swallowing difficulty for arm 1 and 17% in the other arm.

The depression and anxiety scores of HADS are of primary interest. Consider the change score between baseline and 12 weeks after the start of radiation therapy. With 150 in each of the two remaining arms, one has 85% power to detect an effect size of 0.419 s.d. unit on the scale of change score using a two group t-test at a significance level of 0.01.

Quality-adjusted life years (QALY) is calculated as EQ-5D utility score weighted survival time. For the purpose of power calculation, consider a patient with a QALY greater than 12 weeks as “success” and less than 12 weeks as “failure.” With a size of 150 patients having EQ-5D score at baseline and 12 weeks, we have 90% power to detect a 20% difference of 12-week success rate, assuming the 12-week success rate is 65% for arm 1 (45 Gy) and 85% for the remaining experimental arm.

Hypothesis C

The different treatment arms have different dose schedules for different lengths of times, which may impact the satisfaction with treatment due to the inconvenience posed. Patients with an inconvenience rating of 1 or 2 will be defined as “Inconvenient” and those with a rating of 3 or 4 as “Convenient.” If the remaining experimental arm is arm 2 (70 Gy), with 150 patients having inconvenience measure on each arm at baseline and 12 weeks after the start of radiation therapy, a two group continuity corrected Chi-square test at a significance level of 0.05 will have 81% power to detect the 16% difference of the proportion of patients reporting treatment inconvenience between the two remaining study arms, assuming 60% of patients in arm 1 report treatment inconvenience and 76% of patients in arm 2 report inconvenience. If arm 2 is discontinued after 30 patients have been accrued to the main study, with about 150 patients in arm 1 and 15 patients in arm 2 having complete assessment at baseline and 12 weeks, we will have 74% power to detect the 30% difference of the proportion of patients reporting treatment inconvenience between the two remaining study arms, assuming 60% of patients in arm 1 report treatment inconvenience and 90% of patients in arm 2 report inconvenience.

Analytic Methods:

For continuous HRQOL (Health-Related Quality of Life) scores, including Physical Well-Being, Functional Well-Being, Lung Cancer Physical Symptoms subscale scores from the FACT-TOI, Eating and Swallowing subscale scores from the FACT-Esophagus Subscale, and depression and anxiety subscale scores from HADS, two-group t test and analysis of covariance will be the primary method used to analyze and test the planned comparisons for the change scores from baseline to 12 weeks after the start of radiation therapy with and without adjusting for other prognostic factors. In analysis of covariance, in addition to study arm, significant baseline prognostic factors will be included in the model to adjust for confounding effects. These planned tests results will be reported at the significance level designated in the section of power analysis. Similar exploratory univariate analyses will be conducted for the change score from baseline to other assessment points at 3, 5, 7, 26, and 52 weeks after the start of radiation therapy. Multivariate analyses for evaluating the trend of HRQOL scores varying over time will be conducted using a linear mixed effect model and linear model with generalized estimating equation (GEE) with all valid measures from multiple time points included in the analysis.

For binary dichotomized endpoints, such as ECOG esophagitis severity (severe/ ≥ 7 vs moderate/ < 7), difficulty swallowing (severe/ ≥ 4 vs. moderate/ < 4) and ordinal endpoints, such as treatment inconvenience (inconvenient/ ≤ 2 yes vs. convenient/ ≥ 3), Chi-square test and generalized linear model with a logit or multi-logit link will be used to test the planned comparisons. In regression analysis, baseline prognostic factors besides study arm will be included. Again, these planned tests will be reported at the significance level as designated in the section of power analysis. Similar multivariate analyses for evaluating the trend of HRQOL scores varying over time will be conducted using a nonlinear mixed effect model and generalized linear model with generalized estimating equation (GEE) with all valid measures from multiple time points included, in which logit link for dichotomized scores and multi-logit link for ordinal scores will be specified. In the analysis of ordinal scores, proportional odds assumptions will be tested.

It is expected that a proportion of quality of life data collected at follow-up assessments will be missing due to various reasons, including failing health of patients. However, the percentage is expected to be less than 10% above and beyond that missing due to death. If the dominant missing mechanism is missing completely at random (MCAR) above and beyond the effect of study condition assignment, then the results based on complete data analysis will be unbiased. However, sensitivity analyses using different statistical methods and assuming different missing mechanisms (MCAR, MAR and NMAR) will be used to evaluate the robustness of main study findings from multivariate data analyses.

The quality-adjusted overall survival will be calculated for each study arm based on the utility score from EQ-5D and the subgroup difference will be tested using the method developed by Zhao and Tsiatis [93].

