5.6 Registration to Companion Studies

There are two substudies within CALGB 30610. The correlative science study must be offered to all patients enrolled on CALGB 30610; the quality of life study must be offered to all English-speaking patients enrolled on CALGB 30610 (although patients may opt to not participate). These substudies do not require separate IRB approval. **Note: The quality of life substudy, CALGB 70702, closed to accrual on August 30, 2017. Therefore, no further patients will be enrolled on the quality of life substudy.**

The substudies included within CALGB 30610 are:

- CALGB 150712: Correlative Science Studies in CALGB 30610 ([Section 10.1](#))
If a patient answers "yes" to "My specimen(s) may be used for the research described above" question #1 in the model consent, they have consented to participate in the substudy described in [Section 10.1](#). The patient should be registered to CALGB 150712 at the same time they are registered to the treatment trial (30610). Samples should be submitted per [Section 6.3](#).
- CALGB 70702: Quality of Life Studies in CALGB 30610 ([Section 10.2](#))

As of August 30, 2017, accrual to CALGB 70702 has been met. **Therefore, after August 30, 2017, not further patients will be registered to CALGB 70702.**

Only English-speaking patients may participate in the QOL companion. If a patient answers “yes” to “I choose to take part in the Quality of Life study and agree to complete the Quality of Life questionnaires” question #5 in the model consent, they have consented to participate in the substudy described in Section 10.2. The patient should be registered to CALGB 70702 at the same time they are registered to the treatment trial (CALGB 30610).

Note: Patients that are registered on CALGB 30610 after they receive one cycle of chemotherapy are NOT eligible for the companion studies.

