15.3 Sample Size with Power Justification

This randomized phase III study is to determine the efficacy of 70 Day QD RT (arm 2) or 61.2 Gy concurrent boost RT (arm 3) as compared to the standard therapy 45 Gy BID RT (arm 1) in patients with limited small cell lung cancer. The primary endpoint is overall survival, which is measured from the date of randomization to the date of death from any cause.

The implementation of the study will be divided into two stages. In the first stage, eligible patients will be randomized with a 1:1:1 allocation to arm 1, 2 and 3. The toxicity profiles of two experimental arms (arm 2 and arm 3) will be analyzed after 30 patients have been treated to each of the experimental arms. If no statistically significant difference of adverse events is found between experimental arms, additional 20 patients will be treated by each experimental arm. The pattern will be repeated until a significant difference is found or 70 patients have been treated by each experimental arm, whichever comes first. In the second stage, after the decision of dropping the experimental arm with higher toxicity is made, the study will continue with two remaining arms with 1:1 allocation. All randomization will be made using a permuted-block scheme, stratified by gender (female vs. male), ECOG PS (0 vs. 1 vs. 2), weight loss within 6 months before entry (weight loss $\leq 5\%$ vs. $> 5\%$), radiotherapy technique: IMRT vs. 3D, timing of first chemotherapy treatment (prior to randomization vs. post-randomization with the start of radiotherapy on the first cycle vs. post randomization with the start of radiotherapy on the second cycle), and chemotherapy backbone (carboplatin vs. cisplatin) [82]. In the end, the study will

randomize 303 patients to arm 1, 303 to Arm 2 and 30-70 patients to the discontinued experimental arm. As of November 20, 2012, the discontinued experimental arm (Arm 3) randomized 88 patients due to a delayed final toxicity interim decision. With an allowance of 5% of patients canceling or ineligible for randomization, the study will accrue a total of 729 patients over a period of 6 years at about 10 patients per month. All randomized patients will be followed for at least 2.5 years after enrollment

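### The quality-of-life companion's arm split (188/188/18) was not updated for the 88 patients randomised to the discontinued arm, so the stated power rests on an inconsistent 150 completers per arm

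*Combined protocol and SAP*

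**What the plan says.** Section 15.7 (Overview) sets the size of the companion: "The companion will register 415 patients (57%) from the 729 patients consenting to the main treatment study". Of these, "394 patients are expected to meet the eligibility criteria", and of the 394, "188 patients are expected in each of the two remaining study arms and 18 patients are in the discontinued study arm". The power analysis in the same section applies 80% completion at both baseline and 12 weeks and obtains "150 patients in the two remaining study arms and 15 in the discontinued study arm". The 150 is meant per remaining arm, as the wording under Hypothesis A confirms. Each power statement for the comparison of the two remaining arms uses that 150.

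Section 15.3 plans "303 patients to arm 1, 303 to Arm 2 and 30-70 patients to the discontinued experimental arm" and then reports that, as of November 20, 2012, "the discontinued experimental arm (Arm 3) randomized 88 patients due to a delayed final toxicity interim decision". Section 5.6 says of the companion: "As of August 30, 2017, accrual to CALGB 70702 has been met".

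**The concern.** The two sections describe different trials. Eighteen companion patients out of 88 randomised is 20% participation (18/88). In each remaining arm, 188 out of 303 is 62%. The plan neither states nor explains such a difference, and Section 5.6 has patients registered to the companion at the same time as to the main trial.

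The 18 does fit an arm closed at 30 patients. Section 15.7 still carries that scenario under Hypothesis C: "If arm 2 is discontinued after 30 patients have been accrued to the main study". The 729 and the 57%, however, belong to the updated trial. The Overview therefore pairs a new total with an old split.

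At stake is how the quality-of-life results are read. With the companion's total fixed, every patient in the discontinued arm is one fewer for the planned two-arm comparisons. A null result would be judged against more power than the plan's own figures support.

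**Working it through.** **Inputs.** Section 15.7: 415 registered, 394 eligible, split 188/188/18, 80% completion, two-sided tests, and the effect sizes and alphas below. Section 15.3: 303 + 303 in the remaining arms, 88 in the discontinued arm, 5% allowance, total 729. The 88 is taken as final, as the 729 does.

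**1. Which figures were updated.**
- Total: (303 + 303 + 88) × 1.05 = 694 × 1.05 = 728.7, i.e. 729. The 88 are included.
- Companion share: 415/729 = 0.569, the stated 57%. Eligible: 415 × 0.95 = 394.
- Split: 2 × 188 + 18 = 394. With an arm closed at 30, 30 × 394/(606 + 30) = 18.6. The 18 was not updated.

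**2. Reproducing the stated power at n = 150 per arm** (0.80 × 188 = 150.4).
- Means: two-sample t test, noncentrality d√(n/2), 2n − 2 degrees of freedom.
- Proportions: normal approximation with pooled variance under the null. The continuity correction is applied through an effective n of (n − 1/Δ)²/n, where Δ is the difference in proportions.

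All five results are within 1 point of the stated values (table below).

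**3. Re-splitting the 394 at equal participation.**
- Discontinued arm: 88 × 394/694 = 50. Two other ways of applying equal participation give 88 × 0.57 × 0.95 = 48 and 88 × 188/303 = 55.
- Each remaining arm: (394 − 50)/2 = 172 (range 170 to 173).
- Completers: 172 × 0.80 = 137.6, about 138 (range 136 to 138).

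**4. Power at 138 per arm.** For Hypothesis A the noncentrality falls from 0.397 × √75 = 3.44 to 0.397 × √69 = 3.30. For esophagitis (1/0.18 = 5.56) the effective n falls from 144.44²/150 = 139.1 to 132.44²/138 = 127.1.

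| Comparison | Alpha | Assumed effect | Stated | n = 150 | n = 138 |
|---|---|---|---|---|---|
| A: TOI, eating, swallowing indices | 0.0167 | 0.397 SD | 85% | 84.8% | 81.2% |
| B: HADS anxiety, depression | 0.01 | 0.419 SD | 85% | 84.9% | 81.2% |
| B: esophagitis, difficulty swallowing | 0.01 | 35% vs 17% | 80% | 80.6% | 76.1% |
| B: QALY | 0.01 | 65% vs 85% | 90% | 90.8% | 87.6% |
| C: inconvenience | 0.05 | 60% vs 76% | 81% | 81.6% | 78.0% |

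For QALY the alpha is taken as 0.05/5, since Section 15.7 counts it among five Hypothesis B comparisons. At 138 per arm, the effect detectable with 85% power for Hypothesis A is 0.415 SD instead of 0.397.

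**5. Lower end of the range.** Taking 55 patients in the discontinued arm gives 135.8 completers per arm. Calculated at 135, power is 80.2% (A), 80.1% (HADS), 74.9% (esophagitis and swallowing), 86.6% (QALY) and 77.0% (C).

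**6. Completion that restores 150.** 150/172 = 0.87.

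**The case against.** A reader might infer that the companion failed to deliver 188 eligible patients and 150 completers per arm, and that every stated power figure is therefore too high. The documents do not support that, for three reasons.

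- **No counts by arm.** The 57% is a registration target divided by an accrual target, not an observed uptake. Section 5.6 says accrual was met, but not whether that means 415 in total or enough patients in the two remaining arms. The 88 had been on record since November 2012 and the companion closed in August 2017, so closure on the remaining arms cannot be ruled out.
- **80% completion is a floor.** The plan says at least 80%, and Section 15.7 cites completion of 85% off treatment in other trials. With 172 eligible, 85% completion gives 146 completers and power of 83.7% (A), 83.7% (HADS), 79.2% (esophagitis and swallowing), 89.8% (QALY) and 80.5% (C). All are within about 1.5 points of the stated values.
- **Uptake while three arms were open is unknown.** At 40%, the discontinued arm would hold 88 × 0.40 = 35 companion patients. Completers would be (394 − 35)/2 × 0.80 = 144 per arm, and Hypothesis A would keep 83%. Patients with a prior chemotherapy cycle are barred from the companion and were admitted to the trial only from February 2013, shortly before the arm closed. That suggests the discontinued arm's share is above proportional, but it gives no size. A much higher uptake, and a correspondingly larger loss of power, would be a guess.

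These points stand, and they make the loss of power conditional. They do not reconcile 18 with 88, and the plan calculated its own power at 80%.

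**Conclusion.** The inconsistency is established from the text alone: 188/188/18 and 150/150/15 describe an arm closed at about 30 patients, while the trial total and Section 15.3 describe one that randomised 88. The consequence for power is an expectation, not an observation. At equal participation across arms and exactly 80% completion, the power for each comparison is about 2 to 4 points below the stated value. Hypothesis A, the primary quality-of-life hypothesis, keeps about 81%. Esophagitis, swallowing and inconvenience fall below 80%. The effect is modest. It does not touch the survival comparison, and no alpha, endpoint or test changes. The correction is worth making because the figures are wrong as written and cheap to put right.

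**What to change.** In Section 15.7, replace 188/188/18 and 150/150/15 with the actual companion counts by arm: registered, eligible, and complete at both baseline and 12 weeks. The companion is closed to accrual, so the sponsor can tabulate enrolment now, and completers once the assessments are in. The 172/172/50 and 138 used here are conditional estimates and should not be written into the plan. From the actual counts, restate the power or the detectable difference for Hypotheses A, B (including QALY) and C. The passage covering discontinuation of arm 2 after 30 patients can be removed, since arm 2 was retained.

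The cost is editorial. No new patients and no change to conduct or analysis are needed. If participation was roughly equal and completion near 80%, the stated power becomes slightly less favourable.

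### Section 15.7 tests the quality-of-life comparisons by plain Bonferroni; Holm's step-down keeps the same 0.05 family-wise error and recovers power when more than one effect in a set is real

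*Combined protocol and SAP*

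**What the plan says.** The Power Analysis part of Section 15.7 sets the error rule. Each of the three hypothesis sets has its own family-wise 0.05, every test is two-sided, and the plan gives this reason for how the 0.05 is split inside a set: "The Bonferroni method is used to address the issue of multiple comparisons for simplicity and reasonable performance with a small number of comparisons".

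- **Hypothesis A.** "Three planned comparisons will be made to address Hypothesis A": the FACT-L TOI, eating and swallowing scores, each at 0.05/3 = 0.0167. The sizing claim is "85% power to detect an effect size of 0.397 s.d. unit on the scale of change score using a two group t-test".
- **Hypothesis B.** Five comparisons, with 0.05/5 = 0.01 each: ECOG esophagitis, difficulty swallowing, HADS depression, HADS anxiety and QALY.
- **Hypothesis C.** One comparison, at 0.05.

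The sample behind these figures is "150 patients in the two remaining study arms and 15 in the discontinued study arm will have complete HRQOL assessments", meaning 150 in each remaining arm (80% of 188).

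The split is more than a sizing device. The Analytic Methods part of Section 15.7 states twice, once for the continuous scores and once for the binary and ordinal ones, that the planned tests are reported at the levels set in the power section. No step-down or other sequential procedure appears anywhere in the documents.

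**The concern.** Under plain Bonferroni each comparison faces the full 0.05/k threshold however many others in its set have already been rejected. Holm's procedure sets the smallest p-value against 0.05/k, the next against 0.05/(k-1), and so on, stopping at the first failure. It needs no further assumption, controls family-wise error strongly at 0.05 under any dependence, and never rejects less.

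The plan's hypotheses are of the kind where this pays. Hypothesis A expects three scores to favor the same arm. Hypothesis B expects worse esophagitis to carry through to psychological state and QALY. A real difference on the second or later score can therefore be missed with no gain in error control. Section 15.4 adds some weight: if survival is roughly equal, the experimental arm might be preferred for lower toxicity or greater convenience, so tolerability evidence may count. The companion closed to accrual on August 30, 2017 (Section 5.6), so power can no longer come from more patients.

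**Working it through.** **Inputs (Section 15.7).** n = 150 per arm; A: 0.397 SD at 0.0167; HADS: 0.419 SD at 0.01; ECOG esophagitis and swallowing: 35% vs 17% at 0.01; QALY: 65% vs 85%. The QALY paragraph does not restate its level; 0.01 is assumed, as elsewhere in B. The documents give no correlation between endpoints, so common values from 0 to 0.7 are assumed.

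**Step 1. Reproduce the stated powers.**

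*Means:* power ≈ Φ(d√(n/2) − z), with z the two-sided critical value.
- A: 0.397 × √75 = 3.438; 3.438 − 2.394 = 1.044; Φ = 85.2% (noncentral t: 84.8%). Stated: 85%.
- HADS: 0.419 × √75 = 3.629; 3.629 − 2.576 = 1.053; Φ = 85.4% (t: 84.9%). Stated: 85%.

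*Proportions with continuity correction:* effective n* = n(1 − 1/(nΔ))²; power = Φ{[Δ√n* − z√(2p̄q̄)] / √(p₁q₁ + p₂q₂)}.
- ECOG and swallowing: n* = 150(1 − 1/27)² = 139.1; (0.18 × 11.794 − 2.576 × 0.6203)/0.6071 = 0.865; Φ = 80.6%. Stated: 80%.
- QALY: n* = 150(1 − 1/30)² = 140.2; (0.20 × 11.839 − 2.576 × 0.6124)/0.5958 = 1.327; Φ = 90.8%. Stated: 90%.

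All four agree with the plan.

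**Step 2. Power of a single test at each Holm threshold.**

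| Threshold | A | ECOG, swallowing | HADS | QALY |
|---|---|---|---|---|
| 0.01 | – | 80.6% | 84.9% | 90.8% |
| 0.0125 | – | 82.8% | 86.7% | 92.0% |
| 0.0167 | 84.8% | 85.3% | 88.8% | 93.5% |
| 0.025 | 88.1% | 88.6% | 91.5% | 95.3% |
| 0.05 | 92.9% | 93.2% | 95.1% | 97.5% |

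Bonferroni stays on the first row that applies to its set. Holm moves down one row after each rejection.

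**Step 3. Hand check for A, independent endpoints, all three effects real.** Let a = 0.8479, b = 0.8814, c = 0.9288 be the powers at 0.0167, 0.025 and 0.05.
- Bonferroni rejects all three with probability a³ = 0.61.
- Holm rejects all three with probability [b³ − (b−a)³] + 3(c−b)[b² − (b−a)²] = 0.6848 + 0.1103 = 0.795.

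**Step 4. Simulation.** 400,000 draws of correlated normal test statistics, with means set to give the Step 1 powers. Holm results run from correlation 0 to 0.7.

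| Case | Bonferroni, per comparison | Holm, per comparison |
|---|---|---|
| A, all three real | 85% | 92% to 90% |
| A, two of three real | 85% | 88% to 87% |
| A, one real | 84.9% | 85.0% |
| B, all real: ECOG, swallowing | 81% | 91% to 89% |
| B, all real: HADS | 85% | 94% to 91% |
| B, all real: QALY | 91% | 96% to 94% |
| B, only ECOG and swallowing real | 81% | 82% |
| B, one real | 80.7% | 80.8% |

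- Power to reject all three in A rises from 61-73% to 79-84%, and all five in B from 43-65% to 75-84%. The simulated 79% at correlation 0 agrees with Step 3.
- The chance of at least one rejection is the same under both methods, because the first step is the same: 99.7% to 94.5% in A and 99.99% to 96.9% in B with all effects real.
- With no real effect, family-wise error under either method is 4.9% (correlation 0) and 4.5% (0.5) in A, and 4.9% and 4.3% in B. With some effects real, the chance of any false rejection under Holm is at most 4.7%.

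**The case against.** The case for leaving the plan alone has four parts.

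1. **Bonferroni is valid and pre-specified, and the companion is sized for it.** This stands in full. The plan also gives two reasons, not one: simplicity, and adequate performance with few comparisons.
2. **The large gains need every effect in a set to be real at its design size.** This stands as a limit. At 12 weeks the 45 Gy arm is 9 weeks past radiotherapy. The background in Section 10.2 cites accelerated-radiotherapy patients whose esophagitis resolved and whose well-being was back to baseline four weeks after treatment, and a trial with no significant difference in quality-adjusted life years. If effects are mixed, the gain is much smaller.
3. **Bonferroni yields simultaneous confidence intervals directly, and each verdict stands alone.** This stands as a cost. Under Holm all five p-values in B, including the quality-adjusted survival test, must be final together.
4. **Relaxing a rejection rule after accrual has closed needs care.** This stands as a condition on timing. The documents do not say whether comparative quality-of-life data have been examined.

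None of this makes fixed levels the better test, since Holm never does worse on rejections at the same error rate.

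A reader might also infer that strongly correlated scores are where Bonferroni loses most to Holm. The calculation shows the reverse: in A the per-comparison gain falls from about 7 points at correlation 0 to about 5 at 0.7. The gain comes from several effects being real. Nor may 0.419 SD be applied to all five B endpoints; the plan uses it only for HADS.

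**Conclusion.** The point holds as a loss of efficiency, not an error. With all planned effects real, fixed Bonferroni levels give up about 5 to 7 points of power per comparison in A and about 3 to 11 points in B. The loss is 2 to 3 points with two of three effects real in A, 1 to 2 points with two of five in B, and almost nothing with one. These figures rest on the plan's own effect sizes, 150 complete patients per arm and an assumed common correlation of 0 to 0.7.

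Three stronger readings are not supported. The type I error control is sound and the stated powers are correct. The companion is not short of power to find something, because the chance of at least one rejection does not change. The all-three and all-five figures only illustrate the effect, since no section makes winning every comparison a criterion of success.

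Hypothesis C has one comparison and is untouched, as is the overall survival analysis.

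**What to change.** - **Section 15.7, Power Analysis:** state that the planned comparisons within Hypothesis A and within Hypothesis B are tested by Holm's step-down procedure at family-wise 0.05, two-sided. Keep 0.0167 and 0.01 as the sizing levels, so that the stated powers become lower bounds.
- **Section 15.7, Analytic Methods:** change both sentences that tie reporting to the designated levels, so that they refer to Holm-adjusted p-values within each set. Changing only the name of the method would leave contradictory text.
- **Timing:** document the change, and that it was made before comparative quality-of-life results were seen. If they have already been seen, keep Bonferroni as the planned analysis and show Holm-adjusted p-values as supplementary.

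The cost is a few sentences and one extra column of output, with no added patients. Simultaneous confidence intervals become less direct, and each verdict in a set depends on the other p-values in that set.
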